## **Study Protocol**

### ***Study design***

This parallel-group RCT was designed to compare retention days in residential treatment among participants randomly assigned to one of two study conditions as adjuncts to their residential SUD treatment: (1) MMWR and (2) Neurobiology of Addiction (NA), with the latter serving as the psychoeducational control condition. Baseline interviews occurred prior to randomization and post-intervention interviews occurred up to 14 days after the last class session of the study intervention. All participants received SUD treatment services as normally provided by the treatment facility without affecting the level of usual care provided to patients. The study site offered no structured mindfulness-based activities or services during the study period. The University of Southern California Institutional Review Board approved this study (UP-14-00391).

### ***Study site standard care***

The site for the study was a publicly-funded residential treatment facility for women diagnosed with SUD in Southern California. It had the capacity to provide on-site housing and comprehensive services for up to 110 women and their children. Childcare and children's services were provided on-site along with an array of supportive services for pregnant and parenting women. The site coordinated services for women with multiple vulnerabilities, including those with mental health issues, trauma (physical and/or sexual abuse) in their past or present, and/or health problems such as HIV/AIDS. While women could remain in residential treatment for up to 12 months, the average length of stay was 5.5 months. The program included mental health and SUD diagnosis and treatment, bio-psychosocial assessment, chemical dependency education and counseling, individual and group therapy, relapse

prevention, random drug testing, specialized women's groups, trauma education and support, family education and counseling, vocational training, educational support, case management, nutritional education and support, health and wellness activities, and 12-step meetings.

Referrals to the following services were made as needed: medical and dental, domestic violence, psychiatric care, GED classes, and Early Head Start. The residential treatment program was situated on a large 4-acre campus that includes residential quarters, space for group therapy and classes, a computer lab, a nursery, and a classroom for the pre-school program that is provided by the local school district.

### ***Participants and procedures***

Participants were adult women clinically diagnosed with SUD and admitted to the residential SUD treatment program study site. Upon admission, all patients met one-on-one with the site's intake clinician coordinator who conducted an assessment for substance use disorders, mental health disorders, and suicidality using the DSM-5. At that time, the same clinician also completed a psycho- social assessment using an in-house form to identify important aspects of patient history and patient needs to inform case management and treatment plan. The site psychiatrist and on-site clinician coordinator discussed diagnostic assessment, determined final diagnoses, and made record in the patient chart. The site intake counselor verified study eligibility, and for those women who were eligible, informed clients about our study. The names of clients who assented to be contacted by the study team were provided to the study interviewer. The study interviewer made appointments with prospective participants, conducted the informed consent and HIPAA process, and administered the baseline assessment interview. As part of the site's normal post-admission protocol, patients began receiving services as usual including individual and group therapy, psychoeducation groups and other services. Psychoeducation and therapy groups were scheduled on a six-week cycle.

Inclusion criteria for the research trial were: client at the residential treatment study site, female, adult aged 18 to 65 years, diagnosed with SUD via clinical record, fluent in English, and agreed to participate in the study. Exclusion criteria were: inability to comprehend or sign informed consent, cognitive impairment, untreated psychotic disorder or severe chronic mental health condition based on clinical intake LR- DSM-IV or DSM-V diagnostic assessment, older than 65 years of age as this was unusual at the site, reported suicidality during the prior 30 days based on clinical intake assessment, current prisoner, more than 6 months pregnant, and not willing to sign a HIPAA form or be audio recorded during interviews and intervention sessions. Study interventions were held separately two times per week during the same time slot. Study participants joined the first session of their assigned group, which started every six weeks per study site protocol.

To minimize bias across study groups related to participant characteristics and histories, we applied urn randomization as implemented by the Urn Randomization Program (version 1.01) after a group of 10 to 30 women were deemed eligible for randomization. Strata variables were current pregnancy (yes or no) and age (18 to 31 years or 32 to 65 years) to ensure these characteristics were equivalent across groups at baseline because they can affect SUD treatment outcomes. The urn approach is robust against experimental bias in clinical trials because it is a compromise between perfect balance in treatment assignments and complete randomization to eliminate experimental bias.

### *Interventions*

#### ***Moment-by-Moment in Women's recovery (MMWR)***

This intervention was delivered twice weekly for 80 min each for a total of 12 group sessions (6 weeks) during residential treatment. MMWR was guided by an instructional manual with

standardized lesson plans. An experienced teacher trained in both MBSR and MMWR facilitated all sessions along with an on-site masters-level clinician with experience in SUDs who co-facilitated the intervention. Each class session had a central theme divided into five segments in the following general order: (1) welcome, review of group culture, brief homework practice check-in, objectives, and brief mindfulness meditation or practice; (2) didactic psychoeducational presentation and discussion of lesson content; 3) experiential meditation and mindfulness practices related to the session's theme; (4) practice of sitting or walking meditation, body scan, and/or standing stretching; and (5) selected reading related to session topic, assignments for the next class, and closing meditation. Trainees were expected to learn skills to approach experiences and stressors using mindfulness principles. Students learned about the role of automatic reactivity to stressors and its relation to addiction and relapse; the connections between stress, triggers, and relapse; and how to use mindfulness practices to respond best to related thoughts, emotions, body sensations (including those related to stress in a residential treatment setting that could lead to treatment dropout), and triggers while still avoiding relapse. As with MBSR, trainees learned and practiced self-regulation strategies using four foundational mindfulness practices. Teachers instructed on the use of formal (audio- guided sitting meditation, sitting meditation without audio, loving kindness meditation, walking meditation, body scan, and mindful stretching) and informal practices (stop light technique, triangle of awareness, mindfulness of breath, mindfulness of emotions, mind- fulness of thoughts, mindfulness of body sensations, and mindfulness of cravings). Throughout the course, students were encouraged to bring mindful awareness into their daily activities by using informal practices and to engage in formal meditation practices as homework in accordance with practice assignments and guided meditation audio recordings. Participants received a MMWR Participant Workbook at the beginning of the course organized by session, containing key concepts and practices introduced in each session, and homework and practice assignments for each session. Participants were asked to bring their Workbook to each session so that they

could report on the previous week's assignment and the current session's homework and practice assignments could be explained by the facilitator and reviewed as women followed along. Some assignments asked participants for specific reflections and written responses. Participants received a MP3 player with meditation audios for each session to guide participants through practices introduced in each session.

### ***Neurobiology of addiction (NA) psychoeducation attention control***

This intervention was delivered twice weekly for 80 min each for a total of 12 group sessions (6 weeks) during residential treatment. NA was guided by an instructional manual with standardized lesson plans (Amaro et al., 2016; unpublished facilitator's manual). The curriculum was previously developed by [name] over 3 years with input and review from focus groups of women and providers in SUD treatment, and subsequently reviewed by three experts in NA. A masters-level educator with a background and training in the NA facilitated all sessions and an on-site masters-level clinician with experience in SUDs and training in NA co-facilitated the intervention. Participants received didactic education on the structure and function of the brain and the neurobiology of addiction. Although educational and centered on knowledge acquisition, the program has no proven efficacy in altering substance use behavior. It included didactic psychoeducational presentation using PowerPoint, video recordings, exercises, games, and group discussions to reinforce the session content and respond to questions. Sessions did not address behavior change strategies, stress reduction, mindfulness, or relapse-related content. Films, videos, exercises, activities, and discussions were used to explain content and promote participant engagement. Topics included: (1) definition of addiction and why it is a brain disease; (2) brain structures and functions and those related to addiction; (3) effects of various types of substances on the brain; (4) rewarding effects of substances and how these effects lead to addiction; (5) definitions and brain functions related to craving and withdrawal; and (6) the roles of treatment in recovery. Participants were expected to gain knowledge pertaining to

basic brain structure and function and the effects of drugs on both. The intervention was equivalent to MMWR in time, teacher attention, expectancy of benefit, and group support. Participants received a NA Participant Workbook organized by session that included session specific information covered in each session such as selected PowerPoint slides and were asked to bring these to class to help them identify questions they had from the previous session. Participants received MP3 players with audio clips of key sections of videos introduced in class.

Women's Treatment and Early Recovery (MBRP-W)

NCT02977988

June 02, 2021

Statistical Analysis Plan

Measures for data capture

Discharge Status. Following routine site protocol, the SUD site treatment team (i.e., certified SUD counselor, masters-level clinician therapist, and team supervisor masters-level therapist; the latter two registered with the Board of Behavioral Sciences) decided on a case-by- case basis if a client developed the necessary skills to complete residential treatment. One of three clinical progress designations was documented in a patient's chart at discharge based on their progress. *Completer:* patient completed course of treatment, met treatment goals and were sufficiently stable (i.e., developed sufficient coping skills, attended groups, adhered to requirements on days away from the facility such as calling in, returning on time and negative drug screen) to transition to stepped-down care. *Non-completer with satisfactory progress:* patient left treatment before completion of the treatment plan and be- fore achieving all treatment goals, but deemed by the clinical team as having made important progress toward treatment goals and improved stability. *Non-completer without satisfactory progress:* patient left treatment before completion of the treatment plan and the clinical team determined that little or no progress was made toward achieving treatment goals (i.e., left early in treatment without being able to re- ceive many services, administratively discharged due to multiple oc- casions of relapse as assessed by drug screens without changes in be- havior, repeatedly violated residential treatment rules such as bringing drugs on site). *In-residence:* patient remained in treatment at the residential treatment facility at the end of the analytic period (i.e., day 150). It was not possible to blind the discharge team to group assignment; however, the study was presented to the discharge team as a test of two alternative intervention approaches in an effort to prevent any unbalanced expectation of treatment benefit.

Days until discharge. We used site discharge records to calculate the number of days in residential treatment beginning from the study intervention start date (day 0) and ending at day 150. We selected an analytic time period to approximate the average length of stay at the SUD treatment site (5.5 months).

Data analysis

Power analysis yielded an estimated sample size of 200 to 225 needed to detect a medium-sized effect (hazard ratio = 0.52 to 0.54) for residential treatment retention using a log-rank test with a two- sided 5% significance level and 80% power, given the probability of remaining in the treatment program in the control group is 50%. We conducted standard statistical diagnosis and performed descriptive analyses of background variables, assessed variable distributional properties, plotted means of the continuous outcome variables at each time point, and assessed internal consistency and test-retest reliability of study scales. We verified the adequacy of randomization on demo- graphic and clinical covariates, and identified variables found to differ between groups at $p < .20$ (Table 1) to include them as model covariates. Based on this criteria, the covariates included in all adjusted models were number of mental health diagnoses (i.e., SUD only, 1 co- morbid mental health dx, 2 + comorbid mental health dx), adulthood trauma exposure (LSC-R), PTSD diagnosis by DSM-5, and PTSD symptom score (PSS-SR), as well as a study design feature (i.e., days in residential treatment prior to study intervention start date obtained from clinic records) to account for exposure to residential treatment prior to the start of our study intervention.

To examine the differential risk of the outcome event (i.e., patient left treatment before completion of the treatment plan and made little or no progress toward achieving treatment goals based on clinical team determination), we applied Kaplan-Meier survival analysis using an intent-to-treat (ITT) approach with time starting on the first day of the study intervention and

ending 150 days later. Participants with the discharge status of completer, non-completer with significant progress, and in-residence were coded as 1 for “retention”. Participants with the discharge status of non-completers without significant progress were coded as 0 for “non-retention”. Our examination of the survival curves revealed that group curves crossed at 50 days from the start of the intervention, which indicated the need for a piecewise model. Thus, a multivariable, 2-piece model (i.e., Piece 1 predicting outcome events during day 0 to 50 and Piece 2 predicting outcome events for days 51 to 150) was calculated. The first piece of the model coincided with the study intervention period and the second piece to the post-intervention period. Adjusted Cox proportional hazards regression (PROC PHREG), with days as the time scale, provide estimates of hazard ratios (HR) and the 95% confidence intervals (CI) for the non-retention outcome event. HR effect size estimates are categorized as small (0.77), medium (0.53), and large (0.36) (Amaro et al., 2016). We conducted logistic regression (PROC LOGISTIC) to test for group differences in satisfactory progress among the subgroup of non-completers. We used general linear mixed models (PROC MIXED) to examine differential changes in the self-reported mechanism of action variables from pre-intervention to post-intervention by group, adjusting for covariates. We used Pearson r to test for correlation between class attendance (as a dosage variable) and change in mechanisms of action measure scores. Pearson r effect sizes are small (.10), moderate (0.30), or large (0.50). All analyses were conducted in SAS version 9.4 (SAS Institute). All models used a maximum likelihood estimated approach to account for missingness.

Substance Use and Relapse

To quantify substance use at the three assessment points (baseline, postintervention, and follow-up), our trained study staff used the TLFB measure, which is a comprehensive retrospective calendar-based validated semistructured interview measure of daily substance use (29). From TLFB data, we calculated substance use from study intervention start date

through the day of the last intervention session date (6 weeks later) and from intervention end date to 7 months later (8.5-month follow-up period in total). The interview window for postintervention assessment was 1 to 14 days after the intervention end, and for the follow-up assessment, the window was 7–9 months after the intervention end, and this variability was dependent on participant availability. This allowed for the quantification of daily substance use from study intervention start date to study end point. TLFB data allowed us to operationalize three substance use outcomes for any drug use and alcohol to intoxication as well as methamphetamine and cannabis/marijuana, including the following: time to first use, quantified as days until first any drug use or alcohol intoxication; days of use, quantified as the total number of days in which any drugs were used or alcohol intoxication occurred, and relapse status, quantified according to a) abstinent, did not use during the period after the study intervention; b) lapse, used after study intervention but did not revert to regular use on one-third or less of days after first use; and c) relapse, used substance after the study intervention and continued to use regularly on more than one-third of days from first use.

Alcohol and Drug Use Confirmation Tests

Breathalyzer (for alcohol) and urine (for drug) samples were collected at postintervention and follow-up. We calculated agreement rates for any and each drug (excluding alcohol) against TLFB self-report. Only two participants had a positive Breathalyzer result. For urinalysis, we compared TLFB drug use reports for 3 days before the urinalysis date against the urinalysis result.

Data Analysis

Our analytic sample size of 200 was powered to detect a medium-sized effect (Cox regression hazard ratio [HR] = 0.51) for days until first drug use with a two-sided $p < .05$ significance level,

80% power, and a 35% probability of substance use in the control group. Our ITT analysis of $N = 200$ did not include the 25 women randomized to a study group who never showed up to the first class and were thus excluded from analysis based on receiving no dose of the intervention. Prediction models included clinical covariates identified a priori as having conceptual relevance for their impact on the effect of study intervention on recovery (i.e., number of mental health diagnoses coded as SUD only, one co-morbid mental health diagnosis, two or more comorbid mental health diagnoses, adult- hood trauma exposure [summed domain score from Life Stressor Checklist Revised], PTSD diagnosis via the Diagnostic and Statistical Manual of Mental Disorders [5th Edition], and PTSD symptom score [PTSD symptom Scale Self Report]). These models also adjust for an inherent study design variable (i.e., days in residential treatment before study intervention start date). Unadjusted models as effect size confirmation is located in the online supplement. We use the piecewise Cox regression PHREG procedure in SAS version 9.4 (SAS Institute) to model time periods during and after the study intervention (i.e., piece 1 predicting outcome events during the intervention period and piece 2 predicting outcome events after the intervention). Resulting HR effect sizes are interpreted as small (0.77), medium (0.53), and large (0.36) (35). Next, because of the zero-inflated distribution of days of substance use, we use negative binomial hurdle models to estimate any use (versus abstinence) and days of use among users simultaneously (36). Finally, we compute unadjusted and adjusted proportional estimates for group differences in relapse status (i.e., abstinent, lapse, relapse), and effect size is expressed as odds ratios (ORs).

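### Retention covariates are chosen by baseline imbalance at p < .20, the same four are called a priori for substance use, and the urn factors (age group, pregnancy) are in neither covariate list

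*SAP*

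**What the plan says.** **Retention (SAP, first Data analysis section).** After checking the randomization, the SAP "identified variables found to differ between groups at $p < .20$ (Table 1) to include them as model covariates". On that basis "the covariates included in all adjusted models were number of mental health diagnoses", followed by adulthood trauma exposure, PTSD diagnosis and PTSD symptom score. Days in residence before the intervention is added separately as a design feature, so the p < .20 rule does not account for it. The Kaplan-Meier analysis is described without covariates. The two-piece model is described as multivariable, and the hazard ratios come from this: "Adjusted Cox proportional hazards regression (PROC PHREG), with days as the time scale, provide estimates of hazard ratios (HR". The same section also reports: "Our examination of the survival curves revealed that group curves crossed at 50 days from the start of the intervention".

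**Substance use (SAP, Data Analysis under Substance Use and Relapse).** The same four clinical variables and the same design variable appear, on a different stated basis: "Prediction models included clinical covariates identified a priori as having conceptual relevance for their impact on the effect of study intervention on recovery". For these outcomes, "Unadjusted models as effect size confirmation is located in the online supplement".

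**Randomization (Protocol, Participants and procedures).** "Strata variables were current pregnancy (yes or no) and age (18 to 31 years or 32 to 65 years". The reason given is that these characteristics can influence treatment outcome and should be equivalent between groups at baseline.

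**The concern.** A between-arm p-value at baseline shows how far the arms happen to differ on a variable. It does not show whether that variable predicts leaving treatment. A set built this way depends on the observed allocation and may or may not contain useful predictors.

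The rule also works against the variables with the clearest claim to inclusion. The urn keeps age group and pregnancy close to balanced, so an imbalance screen will tend to pass over them.

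Three things are at stake:
- every retention hazard ratio that the SAP describes rests on the screened set;
- a reader cannot tell when or why the same set was fixed for substance use;
- the two factors that the trial itself named in advance as relevant to outcome are in neither list.

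**Working it through.** **1. The plan's own figure.** The retention sample size is 200 to 225 for HR 0.52 to 0.54, two-sided 5%, 80% power and 50% control retention. Freedman's formula gives events = [(1 + HR)/(1 − HR)]² × (1.960 + 0.842)². N is events divided by the mean event probability, with a treatment-arm probability of 1 − 0.5^HR and 1:1 allocation assumed.
- HR 0.52: 79 events; 79/0.4013 gives N = 197.
- HR 0.54: 88 events; 88/0.4061 gives N = 217.

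This is close to the stated range and is not disputed. At N = 200, expected events are 200 × 0.4037 ≈ 81 for retention (HR 0.53) and 200 × 0.2736 ≈ 55 for substance use (HR 0.51, 35% control events).

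**2. The two covariate lists side by side.**

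| Variable | Retention: stated basis | Substance use: stated basis |
|---|---|---|
| Number of mental health diagnoses | p < .20 imbalance | a priori relevance |
| Adulthood trauma exposure | p < .20 imbalance | a priori relevance |
| PTSD diagnosis | p < .20 imbalance | a priori relevance |
| PTSD symptom score | p < .20 imbalance | a priori relevance |
| Prior days in residence | design feature | design variable |
| Age group | not listed | not listed |
| Current pregnancy | not listed | not listed |

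**3. Can four selections arise by chance?** With k independent candidates and sound randomization, the number passing is binomial(k, 0.20). The text does not give k. For k = 10, 20 and 30 (assumed), 2, 4 and 6 are expected to pass, and the probability that at least four pass is 12%, 59% and 88%. Four selections need not signal anything beyond chance.

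**4. Does the rule tend to miss the urn factors?** Simulation: 225 randomized by urn(1,1), half in each age group, 10% pregnant (all but the 225 assumed). Each urn factor passes p < .20 in about 5% to 6% of trials, and at least one passes in 10% to 12%. Under simple randomization the figures would be 20% and 1 − 0.8² = 36%.

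**5. What difference do the urn factors make?** As in step 4, with 25 of the 225 removed at random and 8,000 replicates per cell. PTSD score and prior days are assumed prognostic at HR 1.3 per SD. Power (%) at an assumed stratum HR of 1.0 / 1.5 / 2.0:

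| Outcome | Unadjusted | Listed set | Listed + urn factors | Design factors only |
|---|---|---|---|---|
| Retention, HR 0.53 | 77.7 / 77.1 / 75.0 | 79.2 / 79.2 / 76.9 | 79.2 / 80.5 / 80.3 | 78.8 / 79.4 / 79.2 |
| Retention, HR 1 to day 50, then 0.53 (test of piece 2) | 53.2 / 52.8 / 50.1 | 55.0 / 54.4 / 51.7 | 55.1 / 55.3 / 53.8 | 54.5 / 54.4 / 52.7 |
| Substance use, HR 0.51 | 66.5 / 66.1 / 64.5 | 68.1 / 67.5 / 66.1 | 68.1 / 68.4 / 68.7 | 67.2 / 67.7 / 67.9 |

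- Design factors only minus listed set: from 67.2 − 68.1 = −0.9 to 79.2 − 76.9 = +2.3 points.
- Listed + urn factors minus listed set: 0.0 to +3.4 points. Part of this is a null rejection rate 0.1 to 0.7 points higher. With critical values calibrated to 5%, the changes are −0.4 / +0.4 / +2.3 (retention), −0.4 / −0.7 / +0.9 (piece 2) and −0.5 / −0.2 / +0.5 (substance use).
- Type I error, design factors only: 4.9 / 5.2 / 5.2, 4.4 / 4.8 / 4.7 and 4.8 / 5.4 / 4.2, so 4.2% to 5.4%. The Monte Carlo standard error of a 5% rate is √(0.05 × 0.95/8,000) ≈ 0.24 points.

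**6. Direction of the effect of omitting a balanced factor.** In a linear model with N = 200 and exact balance on a binary factor, at factor-outcome correlations of 0, 0.2, 0.3 and 0.4 (assumed), type I error is 4.9%, 4.7%, 4.0% and 3.3% if the factor is omitted and about 5% if it is included. Omission makes the test conservative. The urn balances only approximately and the trial uses Cox models, so this shows direction only.

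**The case against.** The p < .20 rule is openly stated, and the four variables are clinically plausible. Kaplan-Meier and the unadjusted substance-use models already avoid the screened set, and the reference to adjusted models leaves room for unadjusted ones. All of this stands. The gap that remains is that no unadjusted retention hazard ratio is named.

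Imbalance among the women analysed may not be pure chance, because the substance-use analysis "did not include the 25 women randomized to a study group who never showed up to the first class". If the screen was run on the women remaining, that is possible. It is a reason to keep the adjusted model in view, but not to make it the only source of retention hazard ratios.

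The numerical effect is small. Five of the nine calibrated changes in step 5 are negative, the only one above 1 point needs a stratum HR of 2.0, and most are of the order of simulation error. This too stands.

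Stronger readings are tempting, and the documents do not support them:
- *The screen costs this trial power.* In simulated pools of 10 or 20 candidates with four prognostic, it lost about 1 to 7 points against a fixed set with two of four prognostic. Those pools are hypothetical. The trial's four covariates are known, and their value depends on how well they predict outcome, which the documents do not show.
- *The screen inflates false positives.* In the same pools, type I error was 4.3% to 4.8% with independent candidates and 6.0% to 7.8% at correlation 0.4. The number and correlation of the trial's candidates are not given, and Table 1 is not in the supplied text, so neither figure can be assigned to this trial.
- *The a priori description is untrue.* It may mean fixed before the substance-use analysis. The SAP does not say so, but nothing in it rules that out.

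**Conclusion.** The point holds as one of credibility, with at most a small change in efficiency. The textual facts are certain: one set of four covariates has two stated origins, the urn factors are in neither list, and retention hazard ratios are described only from adjusted or multivariable models.

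The size is modest: −0.9 to +2.3 points of power for the design-factor model against the listed set, and −0.7 to +2.3 calibrated points for adding the urn factors to that set. These figures rest on assumed stratum frequencies, stratum effects and covariate effects. N = 200 is also an assumption for retention: the SAP states it as the analysed number only for substance use, and for retention gives only a required size of 200 to 225. No false-positive inflation is claimed, and the omission of the urn factors does not invalidate the tests.

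**What to change.** 1. Name one lead Cox model for retention and one for time to first use, each adjusted for the design factors only: age group (18–31 / 32–65), current pregnancy and prior days in residence.
2. Report the unadjusted retention hazard ratio, as is already done for substance use.
3. Keep the existing adjusted model as a sensitivity analysis, labelled as using covariates selected on observed baseline imbalance. Do not choose a new clinical set now: the SAP shows that the survival curves had been seen, so a new choice would also be post hoc. Age group and pregnancy were fixed as factors at randomization.
4. Reconcile the two Data Analysis sections by stating how and when the four clinical covariates were chosen.

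The cost is SAP wording and re-run models; both urn factors were recorded in order to randomize. They add two parameters, but the lead model has three covariate terms, against six in the listed set if number of diagnoses enters as two indicators. Pregnancy may be too sparse for some secondary models; the SAP should say where it cannot be included.
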